5.8 Packaging

The study medications will be dispensed in sterile multi-dose eye droppers of 3 ml volume, which will be used as single-dose applications. One drop of the placebo/ drug solution will be administered to each eye. Therefore 4 eye droppers will be required per day. At each visit, subjects will receive 56 sterile multi-dose eye droppers that will be used as single-dose applications. The eye droppers will be placed in a dark (brown) colored packet before being dispensed to the subject. A label with abbreviated information will be placed on each eye dropper. The zip-lock packet will include the subject's name, stage of visit, instructions for drug use and storage and the drug expiration date. The label will also include the study name (abbreviated) and a statement that the drug is **investigational** for use only in this research study." The first dose will be administered to the patient by the researcher from one of the eye droppers that will be dispensed to the subject at the first treatment visit (visit 2, day 1). No separate packing will be done for the study medication to be used in the MD's office. The subjects will receive the week's remaining doses in a dark packet with an ice pack to take home. Fifty-six sterile eye droppers will be dispensed at each visit.

5.9 Receiving, Storage, Dispensing and Return

5.9.1 Receipt of Drug Supplies

The UIC Investigational Drug Service (IDS) will order the study drug. The study drug will be stored in the Taylor Street/ EEI pharmacy and dispensed to subjects as needed.

5.9.2 Storage

Study medication will be stored at EEI pharmacy until such time as a subject visit is scheduled. The study medication will be directly dispensed to the subject from the EEI pharmacy on each treatment

visit, except for the first dose that is administered in the clinic under the supervision of research personnel. The study medication will not be stored in the MD's office, except when a subject receives his/her first dose, when the medication may be kept in the MD's office for a maximum of 2- 3 hrs in the ice pack provided by the EEI pharmacy.

5.9.3 Dispensing of Study Drug

At the first treatment visit (day 1), the first study medication dose will be administered to the subject in the clinic and eye droppers sufficient to last for 2 weeks will be given to them to take home. The subjects will be asked to return the used and unused eye droppers at the follow- up visits. We will then retrieve the previously -dispensed eye droppers and a fresh 2 week supply will be dispensed by the pharmacy. This will continue from week 2 to week 8. No new drug eye droppers will be given on the 6th (week 8) visit.

5.9.4 Return or Destruction of Study Drug

At the completion of the study, there will be a final reconciliation of drug ordered/ received, drug consumed, and drug remaining. Any discrepancies will be investigated, resolved, and documented. The used drug eye droppers will finally be disposed by the pharmacy according to the pharmacy standard protocols.

6 Study Procedures

6.1 Patient Recruitment and Screening

Prior to recruitment of any patients into the study, written approval of the protocol and informed consent will be obtained from the Institutional Review Board (IRB).

Potential subjects will be recruited from the clinical practice of the investigator at the time of their eye examination visit. The clinical practice is located at the Department of Ophthalmology and Visual Sciences, Eye and Ear Infirmary, [name]. Patients with established Dry Eye Disease (for at least 6 months with annoying or activity limiting visual symptoms) will be approached by a member of the research staff to determine if the patient might be interested in participating in a research study. If the patient is interested, the research staff member will describe the study. If the patient is willing to enter the study, the study will be discussed and the patient will be asked to sign the informed consent form. Consent will be obtained prior to screening to determine eligibility. Subjects will be screened for eligibility, as per the inclusion/ exclusion criteria, and as detailed in section 6.5.1. Eligible patients will be enrolled in the study.

6.2 Assignment of Patient Identification

A study identification (ID) number will be assigned to each subject at screening. This study ID number will be used on all study-related documents. To maintain confidentiality, the subject's name will not be recorded on any study document other than the informed consent form. The master code list will link the subject MRN to the study ID number given to each subject. The master code list will be stored on the desktop in PI's OFFICE in Lions of Illinois Eye Research Institute (LIERI). The data collected and master code list will be accessible only to the PI and the research team involved in this project. The desktops will be password protected as well. Data will not be shared over the internet and will remain password protected. Confidentiality will be maintained. Data will be de-identified once study is completed and for subjects determined to not meet eligibility criteria or who later decline participation in the consent process.

6.3 Screen Failure

A record of screen failures and the reasons for non-eligibility to the study will be maintained.

6.4 Patient Enrollment

Patients meeting the enrollment criteria (see Sections 4.1 and 4.2) will be eligible for the study.

6.5 Study Assessments

The following detailed procedures are performed at the designated clinic visit. All results will be documented on the subject's medical/research charts, source documents, and CRFs as required. All ophthalmic procedures will be performed on both eyes.

6.5.1 Visit 1 Screening

Day -18 to 0

After obtaining informed consent, the following assessments will be performed within fourteen days prior to the subject receiving the first dose of study medication:

- Demographic information including: birth date, gender, race or ethnic origin.
- Medical History including prior medication use and prior procedures: Medical history will be obtained by interviewing the subject and will include a review of the following systems: cardiovascular, dermatologic, gastrointestinal, genitourinary, musculoskeletal, neurologic and respiratory. An allergic history (including medications and food), substance abuse history (including alcohol) and a history of medication use (including prescription, OTC, and herbal products) during the past 30 days will also be completed.
- Ophthalmic and Dry Eye Disease history including: date when the Dry Eye Disease began, verification that the subject has had Dry Eye Disease for at least 6 months, medications used by the subject to treat Dry Eye Disease, previous procedures to treat Dry Eye Disease.
- Ophthalmic Examination (slit lamp examination, Ocular surface redness score, Rose Bengal staining, and a Schirmer 1 test)
- Pregnancy test (urine), if applicable. Women of reproductive age will be asked to use a method of birth control that is acceptable to the subject and the study doctor. This may include oral contraceptive pills, birth control implants/shots or patches, barrier methods or abstinence. Women of reproductive age will not be included in the study if they refuse to use any birth control measure, including abstinence.

Patients currently treating DED with corticosteroids and/or Restasis will stop these treatments during a wash-out period (2 weeks before the start the study drug) and during the whole study. The study doctor will provide advice about decreasing DED symptoms with artificial tears, eyelid massage, or warm compresses.

If the patient agrees to enter the study, the first treatment visit will be scheduled. If a washout period is needed, Visit 2 will be after 2 weeks (\pm 4 days). If a washout period is not necessary, Visit 2 can be scheduled any time in the next 2 weeks after the Screening Visit.

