4.1 Inclusion Criteria

Patients will be eligible for the study if all of the following criteria are met:

1. Aged 18 years or older.
2. Capable of giving informed consent and does provide informed consent.
3. Documented Dry Eye Disease for at least 6 months.
4. Schirmer I <10
5. Corneal/ conjunctival (Rose Bengal) staining ≥ 1
6. Ocular symptoms must be considered as annoying or activity limiting (OSDI ≥ 13 ; mild).
7. Women must be post-menopausal ≥ 1 year, or surgically sterilized. If not, a negative urine pregnancy test is required within 14 days of receiving her first dose of test medication (placebo/ study drug) along with definite evidence of contraceptive use during the duration of the study. Women of reproductive age should use a method of birth control that is acceptable to the subject and the study doctor. This may include oral contraceptive pills, birth control implants, barrier methods or abstinence. If a subject mentions she suspects she may be pregnant after being enrolled, another pregnancy test will be administered. If the test is positive, she will be discontinued from the study immediately.

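### For subjects needing washout, the Visit 2 window in section 6.5.1 can overrun that section's own fourteen-day screening limit and can cut the 2-week washout short

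*Combined protocol and SAP*

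**What the plan says.** Section 6.5.1 contains several timing statements that bear on the same interval:

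- Its heading gives the visit as Day -18 to 0.
- The assessments listed under it, including the urine pregnancy test, Rose Bengal staining and Schirmer test, are to be done "within fourteen days prior to the subject receiving the first dose of study medication".
- Patients on corticosteroids or Restasis "will stop these treatments during a wash-out period (2 weeks before the start the study drug", and they stay off them throughout the study.
- "If a washout period is needed, Visit 2 will be after 2 weeks", with a tolerance of 4 days either way. The sentence does not say what the 2 weeks are counted from.
- For everyone else, "Visit 2 can be scheduled any time in the next 2 weeks after the Screening Visit".

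Section 6.5.2 gives the first dose at Visit 2. Inclusion 7 in section 4.1 separately says that, for women who could become pregnant, "a negative urine pregnancy test is required within 14 days of receiving her first dose". The schedule of visits has one Screening column and shows the pregnancy test only there. The Visit 2 list in section 6.5.2 does not include it.

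The washout is 14 days in section 1.5 and 2 weeks in sections 4.2 (exclusion 6) and 5.6, none of which states a tolerance. Sections 4.2 and 5.6 count it to enrollment, a date that the protocol does not define. Only section 6.5.1 counts it to the start of study drug.

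**The concern.** A window that runs 4 days either side of 14 cannot sit comfortably between a rule that something be at most 14 days old and a rule that something else last at least 14 days. A site booking Visit 2 anywhere in the permitted window could find on the day that the pregnancy test is out of date, with no retest in the schedule. It could also find that the washout has been shorter than the protocol says it should be.

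The first matters for safety and eligibility at first dosing. The second matters because section 5.6 withholds cyclosporine on the ground that overlapping anti-inflammatory action would make any benefit hard to attribute. A short washout could leave some residual effect in the Day 1 OSDI and redness baselines. The documents give nothing from which to size that effect.

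**Working it through.** **Inputs.** From section 6.5.1: assessment limit 14 days, Visit 2 at 14 ± 4 days for washout subjects, washout 2 weeks (14 days) before study drug. From inclusion 7 in section 4.1: pregnancy test within 14 days of first dose. From section 6.5.2: first dose at Visit 2.

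**Reading used.** One screening visit, with the drug stopped there and the interval counted from it. One visit is the natural reading, because section 6.5 says that "The following detailed procedures are performed at the designated clinic visit", the schedule has a single Screening column, and section 6.5.1 refers to the Screening Visit in the singular. Stopping at that visit is natural because consent comes before screening and the instruction to stop sits under Visit 1. The starting point of the count is an assumption, since the washout sentence gives none.

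**The plan's own figure.** 14 + 4 = 18, which matches the Day -18 in the heading. The heading and the Visit 2 window therefore agree with each other. The fourteen-day sentence disagrees with both.

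**Check.** The window is 14 − 4 = 10 to 14 + 4 = 18, that is 9 days.

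| Visit 2, days after screening | Number of days | Assessments and pregnancy test at most 14 days old | Washout at least 14 days |
|---|---|---|---|
| 10 to 13 | 4 | met | not met (10 to 13 days) |
| 14 | 1 | met | met |
| 15 to 18 | 4 | not met (15 to 18 days) | met |

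So 4 of the 9 days fail the assessment limit, another 4 fail the washout, and 1 meets both. At the far end the scheduled pregnancy test is 18 days old, which is 18 − 14 = 4 days beyond inclusion 7.

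**Subjects not needing washout.** Their Visit 2 falls 0 to 14 days after screening, so the fourteen-day limit is always met and no washout rule applies.

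**The case against.** The strongest reply is that each half of the conflict depends on a reading that the text does not force.

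- *Split screening.* If consent and the drug stop came around Day -18 and the assessments were done later, the overrun would disappear. No section describes a second screening attendance, so this is possible but less natural.
- *Starting point.* This objection stands as a limit on the point. If the 2 weeks run from a drug stop before screening, the overrun shrinks. With a stop 4 days earlier, Visit 2 falls 10 − 4 = 6 to 18 − 4 = 14 days after screening, and nothing is overrun. The shortest washout would still be 10 days. If instead the count runs from screening and the drug was stopped earlier, the washout shortfall shrinks but days 15 to 18 still overrun.
- *Tolerance.* The 4 days are attached to the 2 weeks in the sentence about washout, so they may be meant as a tolerance on it. That would excuse days 10 to 13. Sections 1.5, 4.2 and 5.6 do not say so, and it would not help days 15 to 18.
- *Inclusion 7 still governs.* Section 6.4 says "Patients meeting the enrollment criteria (see Sections 4.1 and 4.2) will be eligible for the study", and section 4.1 says "Patients will be eligible for the study if all of the following criteria are met". A site following these must retest before dosing, and nothing forbids an unscheduled urine test.

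A reader might infer that the protocol permits dosing without a valid pregnancy test. It does not; what is missing is the scheduled step that would secure one. A reader might also infer that exclusion 6 is breached on days 10 to 13. That follows only if enrollment means Visit 2, which the protocol does not say.

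**Conclusion.** The point holds as an internal inconsistency in section 6.5.1, of minor severity. The clash between fourteen days and an 18-day heading and window is plain on the page. Its consequences (4 of 9 days over the assessment and pregnancy-test limits, 4 of 9 short on washout) rest on a single screening visit, with both the drug stop and the count taken from it. The washout part further assumes that the 4 days are not a tolerance on the washout.

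Two stronger conclusions are not supported. The rules are not impossible to meet together, since day 14 satisfies them all; the protocol simply does not direct sites to it. Nor is the treatment comparison biased: the window is the same in both arms, and subjects and research staff are masked. The number of subjects needing washout is not stated, so the number affected cannot be estimated.

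**What to change.** (a) Replace the two-sided tolerance with a one-sided window for washout subjects: Visit 2 at 14 to 18 days after the last topical cyclosporine or corticosteroid dose, and no later than 18 days after screening.

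(b) Do the urine pregnancy test at Visit 2 before dosing, or repeat it there if the screening test is more than 14 days old. Add it to the schedule of visits and to section 6.5.2.

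(c) State that the washout in exclusion 6 and section 5.6 is counted to Visit 2.

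The fourteen-day assessment sentence must also be settled, because (a) alone still leaves days 15 to 18 beyond it. If the limit is extended to 18 days for washout subjects, the protocol should acknowledge what that means. Rose Bengal (part of the primary efficacy endpoint in section 3.2) and Schirmer are scheduled before dosing only at screening. For a subject who stops the drug at that visit, those baselines would be pre-washout values up to 18 days old. The alternative is to keep fourteen days and repeat those two tests at Visit 2 when they are out of date. That gives off-drug values at the price of two extra tests, and the protocol would need to say which reading serves as baseline.

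The cost of (a) to (c) is protocol wording, one schedule entry, an occasional urine test, and the loss of days 10 to 13 for subjects who stop the drug at screening. Those subjects keep days 14 to 18, which is 5 of the present 9.

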6.5.2 Visit 2 Day 1 (*Randomization and First treatment visit*)

Prior to first dose (Baseline)

- Vital Signs (blood pressure taken while subject is relaxed in a sitting position for at least 3 minutes, pulse, temperature, and height and weight (at this visit only).
- Baseline Ophthalmic Examination (slit lamp examination, Ocular surface redness score)
- BSCVA (Snellen)
- OSDI
- Clinical Global Impression, Subject Global Assessment
- Record changes in concomitant medication
- Adverse events since screening visit.

Investigator/designee administers first dose

Post-Dose

- Visual Analogue Scale
- Subjects will be trained on how to self-administer the study eye drops and be given a sufficient supply to last for 2 weeks to take home.
- Subjects will receive a study diary on which to record the day/time of each dose and any adverse effects.
- Post dose evaluation for any adverse effects.

6.5.3 Visit 3: *Week 2 (± 2 days)*

Treatment Visit (after any dose for that day)

- Vital Signs
- Ophthalmic Examination (slit lamp examination, Ocular surface redness score)
- Physical Inspection of the Nose and Oropharynx
- OSDI
- Visual Analogue Scale
- Clinical Global Impression, Subject Global Assessment
- Review the subject's diary and record changes in concomitant medication, deviations from drug schedule and adverse events.
- Subjects will be given study medication, sufficient to last for 2 weeks, to take home.

6.5.4 Visit 4: *Week 4 (± 2 days)*

Treatment Visit (after any dose for that day)

- Vital Signs
- Ophthalmic Examination (slit lamp examination, Ocular surface redness score)
- Physical Inspection of the Nose and Oropharynx
- OSDI
- Visual Analogue Scale
- Clinical Global Impression, Subject Global Assessment
- Review the subject's diary and record changes in concomitant medication, deviations from drug schedule and adverse events.

- Subjects will be given study medication, sufficient to last for 2 weeks, to take home.

6.5.5 Visit 5: Week 6 (\pm 2 days)

Treatment Visit (after any dose for that day)

- Vital Signs
- Ophthalmic Examination (slit lamp examination, Ocular surface redness score)
- Physical Inspection of the Nose and Oropharynx
- OSDI
- Test Substance Tolerance
- Clinical Global Impression, Subject Global Assessment
- Review the subject's diary and record changes in concomitant medication, deviations from drug schedule and adverse events.
- Subjects will be given study medications, sufficient to last for 2 weeks, to take home.

6.5.6 Visit 6: Week 8 (\pm 2 days)

Treatment Visit (after any dose for that day)

- Vital Signs
- Ophthalmic Examination (slit lamp examination, Ocular surface redness score, Rose Bengal staining, and a Schirmer 1 test)
- Physical Inspection of the Nose and Oropharynx
- OSDI
- Test Substance Tolerance
- Clinical Global Impression, Subject Global Assessment
- Review the subject's diary and record changes in concomitant medication, deviations from drug schedule and adverse events.

6.5.7 Visit 7: Week 10 (\pm 2 days)

Follow-Up Visit

- Vital Signs
- Ophthalmic Examination (slit lamp examination, Ocular surface redness score)
- Physical Inspection of the Nose and Oropharynx
- BSCVA (Snellen)
- OSDI
- Clinical Global Impression, Subject Global Assessment
- Review the subject's diary and record changes in concomitant medication and adverse events.

7 Statistical Plan

7.1 Sample Size Determination

Our intention is to have at least 30 subjects in each group (study drug/ vehicle) complete the study. This number is based on published reports of similar randomized clinical trials designed to determine

efficacy and tolerability of a test drug in Dry Eye Disease.³²⁻³⁴ A total of 72 subjects will be enrolled so that even if 20% of subjects are unable to complete the study, we will still remain with the intended number of subjects who complete the study (at least 30 subjects in each group). Subjects will be randomized to either of the two groups (#1, placebo; #2, study drug) as explained in section 5.3. However, all subjects who received at least two weeks of treatment with study eye drops and attended at least the first post-treatment (week 2) follow up visit will be included for analysis.

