Net	Neutrophil extracellular trap
OSDI	Ocular Surface Disease Index
Otc	Over the counter
QID	Four times per day
rhDNase1	Recombinant human deoxyribonuclease I
SAE	Serious Adverse Event
SGL	Subject Global Assessment
SP	Substance P
UIC	University of Illinois at Chicago
VA	Visual Acuity
VAS	Visual Analog Scale

Study Summary

Title	A Phase I/II Randomized Placebo-Controlled, Double-Blind Single-Center, tolerability and preliminary efficacy clinical trial of recombinant human deoxyribonuclease (rhDNase) eye drops in patients with dry eye disease.
Short Title	DNase treatment for dry eyes
Protocol Number	UIC-CNBL-1001
Phase	Phase I/II
Methodology	Double-blind
Study Duration	10 weeks
Study Center(s)	Single-center
Objectives	To evaluate the tolerability and preliminary efficacy of rhDNase1 eye drops in patients with Dry Eye Disease.
Number of Subjects	72 (study drug at least 30, placebo at least 30)
Diagnosis and Main Inclusion Criteria	Men and women ≥ 18 years of age with a diagnosis of established Dry Eye Disease, with Schirmer I < 10 , Ocular surface staining ≥ 1 and OSDI mild (≥ 13).
Study Product, Dose, Route, Regimen	Study drug: rhDNase1 (Pulmozyme®), 0.1% eye drops four times a day for eight weeks. Control: drug vehicle eye drops four times a day for eight weeks.
Duration of administration	8 weeks
Reference therapy	None
Statistical Methodology	Descriptive statistics will be used for all primary and safety endpoints, when appropriate. A Wilcoxon test will be used to compare changes in subjective symptoms from Baseline to follow-up values at 2 weeks, 4 weeks, 6 weeks, 8 weeks and 10 weeks. Primary efficacy measure is the change in the OSDI reported between Baseline and Week 8. Primary safety measure is the proportion of patients at week 8 who were able to successfully complete a full eight weeks of therapy with topical administration four times per day (q.i.d).

1 Introduction

This document is a protocol for a human research study. This study is to be conducted according to US and international standards of Good Clinical Practice (FDA Title 21 part 312 and International Conference on Harmonization guidelines), applicable government regulations and Institutional research policies and procedures.

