3.1 General Design

This will be a Randomized controlled trial, in which a total of 72 patients will be enrolled at 1 clinical site. Subjects will be randomly assigned to one of two groups (#1, #2), with at least 30 subjects per group. Group #1 will be given placebo (drug vehicle- eye drops without rhDNase 0.1%) and Group #2 will be given study drug (rhDNase 0.1%).

Patients with established Dry Eye Disease will be approached by a member of the research staff to determine if the patient might be interested in participating in a research study. If the patient is interested, the research staff member will describe the study. If the patient is willing to enter the study, the study will be discussed and the patient will be asked to sign the informed consent form. Consent will be obtained prior to screening to determine eligibility. Screening procedures include documentation of prior Dry Eye Disease. Eligible patients will be enrolled in the study.

All enrolled subjects will receive their first dose of test medication (placebo/ study drug) on study Day 1 in the doctor's office and after completion of the study assessments, will have the topical eye drops dispensed for self-administration. See Section 5.4 *Preparation and Administration of Study Drug* for details.

Subjects will be provided with diaries to record the time of each dose and will also be asked to record any adverse symptoms. In addition, they will be asked to make a note of any missed doses together with the reason for the omission. Subjects will return two weeks later on Day 14 for further study assessments, thereafter at 4 weeks, 6 weeks and 8 weeks (the last day of treatment), and again at 10 weeks after two weeks of no treatment with study drug for the final study assessments.

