5.3 Method for Assigning Subjects to Treatment Groups

This Randomized placebo-controlled trial will have two study groups. Subjects will be randomly assigned to one of two groups (#1, #2). Group #1 will receive placebo (drug vehicle; control group) and Group #2 will receive study drug (rhDNase 0.1%; test group). We will use a computer-based random code generator (Research Randomizer; <http://randomizer.org/>) to generate 1 set of 72 non-unique, unsorted numbers with a range from 1 to 2 representing the group number (#1 is control group, #2 is test group). Each subject will be assigned a study identification (ID) number at screening, eg. subject #1, subject #2, subject #3 and so on. Based on the randomizer generated table, subject #1 will receive either placebo (#1 group) or study drug (#2 group). This will be repeated for each subject. For reproducibility purpose, we will document the final randomization schedule and the random SEED number used to generate the schedule. Randomization will be performed by the Illinois Eye and Ear Infirmary's pharmacy, and neither participants nor research staff will be aware of the assigned treatments. The person conducting the randomization will remain masked as well.

The study identification (ID) number will be used on all study-related documents. To maintain confidentiality, the subject's name will not be recorded on any study document other than the informed consent form. The drug vial number will be linked to the patient identification number.

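### Section 7.1: enrolling 72 cannot leave 30 completers in each group after 20% loss; it leaves 57 or 58 in total, about 28.8 per arm

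*Combined protocol and SAP*

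**What the plan says.** Section 7.1 sets a target of at least 30 completers per group. It gives no effect size, standard deviation or power for that target: "This number is based on published reports of similar randomized clinical trials". It then goes from the target to the enrolment number in one sentence. The first half fixes the total and the loss rate: "A total of 72 subjects will be enrolled so that even if 20% of subjects are unable to complete the study". The second half says what is promised at that loss rate: "we will still remain with the intended number of subjects who complete the study (at least 30 subjects in each group".

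The same section, and section 7.3, define the analysis population more widely than completers: two weeks of treatment and attendance at the week 2 visit are enough. Section 8.1 allows, but does not require, replacement of subjects who withdraw because of an adverse event.

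The Study Summary gives the number of subjects as "72 (study drug at least 30, placebo at least 30", and section 3.1 describes two groups "with at least 30 subjects per group". Section 5.3 uses a web-based generator "to generate 1 set of 72 non-unique, unsorted numbers with a range from 1 to 2". It states no blocking and no fixed 36:36 split.

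**The concern.** The step from 30 per group to 72 is the only calculation behind the enrolment number, because the 30 itself rests on precedent. The sentence promises a minimum in each group at a named loss rate. A reader would take it that the completer target survives 20% attrition, and would judge retention during the trial against that tolerance. If the true tolerance is lower, the target can be missed while attrition is still inside the range the plan calls safe.

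**Working it through.** **Inputs, all from section 7.1.** Target 30 completers in each of two groups, so 60 in total; enrolment 72; loss 20%.

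**1. Reproducing 72.**
- Multiplying the target by one plus the loss rate: 60 × (1 + 0.20) = 72. This matches the plan exactly.
- Dividing by the proportion retained, which is what a loss allowance requires: 60 / (1 − 0.20) = 75. By arm, 30 / 0.80 = 37.5, rounded up to 38, so 76 for equal arms.

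The plan does not show its formula. The exact match suggests the first form was used, but that is an inference.

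**2. Forward check.**
- 72 × 0.20 = 14.4 losses, so 14 or 15.
- 72 − 14 = 58; 72 − 15 = 57; in expectation 72 × 0.80 = 57.6.
- With equal arms, 57.6 / 2 = 28.8 per arm, which is 30 − 28.8 = 1.2 short.
- Both 57 and 58 are below 60, so no division between the groups gives 30 in each. This conclusion does not depend on how subjects are allocated.

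**3. What 72 can tolerate.** 72 − 60 = 12 losses, and 12/72 = 16.7%. That is an upper limit and not a guarantee, because both arms must also keep 30. For a 36:36 split with a fixed number of losses falling at random (hypergeometric), the probability that both arms keep at least 30 is:

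| Losses | % of 72 | Probability |
|---|---|---|
| 6 or fewer | up to 8.3 | 1.00 |
| 8 | 11.1 | 0.945 |
| 10 | 13.9 | 0.693 |
| 12 | 16.7 | 0.247 |
| 13 or more | 18.1 and above | 0 |

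**4. Whether 75 or 76 restores a minimum.** It restores the total and the average: 75 × 0.80 = 60.0, and 76 × 0.80 = 60.8, or 30.4 per arm. With losses at random, the probability that both arms keep 30 is:
- 38:37 with 15 losses: 0.22
- 38:38 with 15 losses: 0.43
- 38:38 with 16 losses: 0.22

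**5. Effect on precision.** Interval width scales with 1/√n, and √(30/28.8) = 1.021, so intervals based on completers would be about 2% wider.

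**6. Allocation (separate from the error).** If the section 5.3 list is read as 72 independent draws with equal probability, the number assigned to one arm is Binomial(72, 0.5). The probability that it lies between 30 and 42 is 0.875, so one arm is assigned fewer than 30 with probability 0.125 before any dropout.

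**The case against.** The best defence is that little turns on this. The 30 is an intention taken from precedent, in a Phase I/II tolerability and preliminary-efficacy trial. The shortfall is two or three subjects in total. The analysis is not confined to completers, so the number analysed may exceed 57 or 58, and replacement of adverse-event withdrawals could lift the count beyond what 72 allows. All of this stands as a limit on the consequence. None of it makes the sentence true: the promise concerns subjects who complete, replacement is optional and partial, and section 7.1 does not rely on it.

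It is also fair to say that simple randomisation is a valid method and that section 5.3 does not claim to balance the groups. Section 3.1 puts the figure of 30 next to assignment, while section 7.1 makes it a completer target, and the documents do not settle which the Study Summary means. The allocation point is therefore design advice and adds no weight to the arithmetic.

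A reader might also infer that screen failures will use up the list. Section 6.2 says "A study identification (ID) number will be assigned to each subject at screening", and section 5.3 reads the list by subject number. But section 6.5.2 places randomisation at Day 1, and nothing says that a failed screen consumes an entry. Any shortfall from this source would rest on an assumed failure rate, so none is claimed.

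**Conclusion.** The statement in section 7.1 is wrong on its own figures. With 72 enrolled and 20% lost, 30 completers in both groups cannot be reached unless enrolment goes beyond 72. This rests on arithmetic alone. Only the per-arm figure of 28.8 assumes an equal split, and only the probabilities assume losses falling at random.

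Severity is minor. Three stronger readings are not supported:
- **That the trial is underpowered.** The plan states no power or effect size, so no loss of power can be derived from it.
- **That 30 per arm is out of reach with 72.** It remains possible with up to 12 losses, provided both arms keep 30.
- **That 75 or 76 would secure 30 in each group.** These numbers secure the total at 20% loss, and only an average of about 30 per arm.

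**What to change.** Keep 72 and restate the sentence in section 7.1, for example: *72 enrolled gives 57 or 58 completers (about 29 per arm on average) at 20% loss; 30 completers in each arm is possible only with at most 12 losses in total (16.7%), and only if the split and the losses leave at least 30 in each arm.* This costs one sentence and makes the stated completer number slightly less favourable.

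If the 20% tolerance matters more than the number 72, enrol 75, or 76 for equal arms. State the result as 60 completers in total and an average of 30 per arm. The cost is three or four more subjects and a longer randomisation list.

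Optional, and not a repair of section 7.1: with enrolment at 72, replace the unrestricted list in section 5.3 with a pharmacy-held 1:1 permuted-block list of varying block sizes summing to 36:36, used in order of randomisation at Day 1. This secures at least 30 assigned per group once all 72 are randomised. It costs a few lines and a new list. The downside is slight predictability, limited by masking and the varying block sizes.
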